4.1 Primary Research Objective

The P³OPPY study is designed to support the American Heart Association's mission to improve maternal/infant health outcomes and address inequities in maternal/infant health care. The promise of DHI and CHW engagement makes P³OPPY interventions potentially transformative, sustainable, and scalable for NHB mothers and their infants from underserved communities in Alabama and beyond. The objective of this pilot study is to determine if it is feasible to randomize and implement DHI and CHW interventions.

4.2 Design Summary

We will challenge existing care paradigms by testing the effectiveness of integrating innovative platforms into the existing healthcare system, including existing DHI and CHW programs from within our consortium, to eliminate critical barriers to equitable healthcare access. After seeking input from a Community Advisory Board, these interventions will be refined and deployed for pilot testing. We will specifically include NHB communities at the highest risk of adverse pregnancy outcomes and which were historically underrepresented in clinical research due to structural racism. Our cross-disciplinary collaboration effectively employs experts across the community, maternal, and infant health continuum. The use of community-based participatory research to tailor the digital health platform and optimize CHW activities/interactions represents a paradigm shift in pregnancy care. Novel technological innovations include the use of secure educational messaging and connection to local resources.

For this pilot, we will randomize a total of 40 eligible participants, 10 to usual care, 10 to DHI, 10 to CHW, and 10 to DHI + CHW

4.3 Eligibility Criteria:

Inclusion Criteria:

- Self Identifies as NHB
- Between 16-49 years old
- 8⁰ - 22⁶ weeks gestational age with a live fetus
- Dating sonogram at <23 weeks gestation
- ADI National 4th or 5th Quintile
- Planning to deliver at UAB Hospital
- Speaks and writes in English
- No indication for delivery at the time of enrollment
- Viable singleton or dichorionic twins

Exclusion Criteria:

- Declines Randomization
- Speaks or writes in languages other than English
- Currently incarcerated
- Fetal demise diagnosed prior to enrollment
- Known major structural chromosomal abnormalities prior to enrollment

4.4 Informed Consent Criteria

Written informed consent will be obtained from all participants. The risks, benefits and alternatives will be reviewed with the patient in detail. An informed consent form will be developed aligning with rules and regulations from the governing Institutional Review Board. A copy of the signed screening consent form will be provided to each participant. Both verbal and written informed consent will be obtained as needed; if this is not possible the patient will not be randomized.

5 Study Procedures

5.1 Overview

With feedback from qualitative interviews and ongoing partnership with the P³OPPY CAB, the DHI and CHW interventions developed in Aim 1 will be piloted in 40 pregnant NHB patients from high ADI (national quintiles 4&5) communities. The interventions will be implemented during pregnancy and will continue after birth until the infant reaches six weeks of life.

5.2 Recruitment and Randomization

All pregnant patients <23 weeks' gestation will be screened for eligibility. The screening will occur in the inpatient and outpatient settings at UAB. In the inpatient setting, patients with limited or no prenatal care frequently present to the obstetric triage unit and/or to the emergency department for pregnancy care, yet this often does not translate to routine prenatal care leading researchers to conclude that these patients are "vulnerable" and "should be considered as a public health strategy worth investigating" [32, 33](#). The OB/GYN team is consulted on all obstetric patients in the ED and obstetric triage unit and a "New OB Lab Panel" is ordered by routine. If this panel is ordered in the ED or obstetric triage unit, a page will be sent to the CWRH research team (on-site 24/7), alerting them to screen the patient for P³OPPY. Additionally, the CWRH team will screen the clinic schedules for potentially eligible prenatal patients in outpatient obstetric clinics. Potential participants will then be approached for enrollment by a trained member of the CWRH team.

The 1:1:1:1 randomization sequence will be uploaded by [name], the Data Coordinating Center lead. Study team will be blinded to the randomization sequence.

5.3 Procedures to Obtain Informed Consent

Written informed consent will be obtained in person for entry into the study. Study staff will disclose the nature and potential risks of participating in the follow-up study. A common consent form template will be used for central IRB submission and adapted to institutional IRB requirements if relevant. This will comply with HIPAA Privacy Rules, and including authorization to obtain and review medical records. After the woman has had the opportunity to review the consent form and has had all questions answered to her satisfaction, she will initial and sign indicating her desire to participate.

5.4 DHI intervention Overview:

We will use a modified DHI developed by Memora Health in conjunction with EQUATE partners at UPenn [22, 23](#). All content is designed for 7th grade Flesch-Kincaid level or lower. We originally planned to utilize an SMS approach grounded by the literature [34-36](#). This approach is utilized by several major US academic centers. Unfortunately, we were informed by UAB legal that patients do not have the ability to consent to this as they interpret this as going against federal law. While we are disappointed in the result and view this as a barrier to improving outcomes for the most vulnerable, we have modified our approach to one approved by UAB legal. Memora will send a text message that has a link that the participant will launch. The educational byte is then launched in a secure browser and the link and message expire in 24 hours.

Education bytes sent by Memora have been modified by the POPPY Study team through a series of bi-directional meetings held over the last year. The participants are sent on average 2 text links per week that have anticipatory guidance during pregnancy, postpartum, and for the newborn through approximately 6 weeks of life / 6 weeks postpartum. There is a possibility you could be followed by this intervention for up to

3 months under qualifying circumstances. The qualifying circumstances are as follows: Intrauterine fetal demise (IUD) and a loss of a baby. The educational bytes are in accordance with the principles published by the American College of Obstetricians and Gynecologists (ACOG). The messages urge the participant to call the OB/GYN clinic or present to the UAB MEU if there are any concerns, and any alerts will be fielded to the POPPY email address covered by our research team during business hours. For example, in addition to the educational texts, a validated depression screen will be shared during pregnancy and postpartum. If the screen is positive, an alert will be emailed to the POPPY Email address and our team member will contact the patient and provide clinical resources. In the rare event that a participant states they are considering suicide, they are instructed to call 988 and to present to the MEU or the nearest emergency room immediately. Additionally, an email is sent to the POPPY email address and our team will follow up with the patient to ensure they sought care.

In addition to the secure educational bytes, the DHI provides appointment-scheduling reminders and the link to KidOne that offers transportation services to pregnant patients, postpartum patients and their infants. In order to provide patients accurate educational bytes, our team will sync with Memora using the secure SFTP platform as recommended by HSIS that will share validated variables such as if the patient delivers, if the patient was diagnosed with preeclampsia, and if the infant is living or deceased.

As this initiative is funded by the American Heart Association with the goal to reduce racial disparities in maternal morbidity and mortality, messages regarding common causes of death including infection, hypertension, hemorrhage, and heart failure are included.

5.5 CHW intervention Overview: The CHW intervention will be adapted from an ongoing CHW program in Jefferson County, AL called “*From Day One (FDO)*”, a comprehensive patient-centered program designed to educate and provide non-clinical, psychosocial, emotional support

Stages	Table 2: CHW Intervention*	
1 st Trimester	Baseline in-person assessment ^{II} ; Education on tobacco, drug and alcohol prevention; Diet and lifestyle education	
2 nd Trimester	Education on breastfeeding and birth control methods; Screenings on food insecurity; Diet and lifestyle education; Environmental Home Assessment	
3 rd Trimester	Host Baby Safety Showers to educate parents about infant safety, prevent childhood injuries, and infant nutrition	
	Maternal Engagement	Infant Engagement
Delivery-associated hospitalization	Follow-up within 48 hours after notification of birth; Breastfeeding support	Vaccine reminders and birth certificate completion support
Postpartum	Reminders to schedule PP visit; family planning / contraception education; PHQ.9; Home environment safety check; Home BP check for patients with HDP	Reminder to register baby for WIC and insurance; Reminder for 1 – 2 week pediatric check-up and immunizations and two months well check-up

*CHWs also engage with client bi-weekly from enrollment until the infant is three months old and is available to assist with Medicaid enrollment, coordinate transportation through Kid One Transport, access to healthy food, access to diaper banks, and is available to attend prenatal and infant visits with the participant according to the patient's wishes. ^{II}Includes vital signs, weight and medical and obstetric history; HDP = hypertensive disorders of pregnancy

to expectant mothers from the 1st trimester of pregnancy through their child's first year of life. FDO was developed and implemented by the Jefferson County Department of Health (JCDH) in collaboration with Connection Health, a non-profit organization in Jefferson County, AL that recruits, trains, and deploys CHWs to address the needs of the most vulnerable communities. CHWs receive 90 hours of rigorous training including >50 hours of in-class instruction, case studies, group work, role-plays, and 20 hours of self-study and assessments. To date, Connection Health has trained over 165 CHWs who have successfully engaged >90% of pregnant mothers enrolled in FDO. In the present study we are collaborating with Connection Health to identify and train CHWs to implement a modified FDO program as part of the CHW and CHW+DHI intervention arms. Table 2 describes the CHW interventions planned which may be modified based on qualitative feedback in Aim 1.

Based on feedback from our interviews and advisory board, participants randomized to the community health worker intervention will be connected to their CHW through the UAB Research team. The CHW will call the participant over the phone to introduce herself, and will offer to meet her at her doctor's appointment (if she desires) or virtually based on the patient's preference. The CHW will reach out to the participant every other week and specific activities are outlined in the enclosed table. Over time, a relationship will develop and it is our goal that the CHW will be seen by the participant as an advocate to navigate the healthcare system.

In other research studies in conjunction with UAB, ConnectionHealth has entered into an IRB Authorization Agreement whereby the UAB IRB is the IRB of record for ConnectionHealth. We plan to use this same IRB structure for the POPPY Study.

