1.5 Purpose of Study Protocol

The purpose of the P3 Providing an Optimized and empowered Pregnancy for You (P³OPPY) study is to evaluate promising interventions to reduce disparities and improve healthcare access and quality among

pregnant women and their infants from historically marginalized communities. The enclosed protocol for the pilot study will assess feasibility of randomization and implementation ahead of the planned clinical trial.

A manual of operations supplements the protocol with detailed specifications of the study procedures.

2. Background

Maternal health disparities in the United States (US) are disturbingly high — The US has the highest maternal mortality (MM) rate – 32.9 deaths per 100,000 live births – among industrialized countries, and Alabama has the third highest MM rate in the US [1,2](#). These starkly high rates are marked by persistent, unacceptable disparities. Unfavorable social determinants of health (SDoH), structural racism, and systemic barriers lead to suboptimal health outcomes in pregnant women from historically marginalized backgrounds [3,4](#). In 2020, the MM rate for Non-Hispanic White (NHW) women in the US was 19.1 deaths per 100,000 births, while the MM rate for NHB women was nearly three times higher at 55.3 deaths per 100,000 live births.¹ MM represents the “tip of the iceberg,” as each death represents numerous “near-misses” that the Centers for Disease Control and Prevention (CDC) captures in a severe maternal morbidity (SMM) composite of 21 outcomes that have profound short and long-term ramifications [5,6](#). As summarized in a review by [name] (P3OPPY Co-PI), NHB women are also more likely to experience each component of the CDC SMM index versus NHW women [7](#).

Our NIH-funded supplement (3UL1TR003096) on racial disparities in maternal mortality identified a significant linear relationship between increasing levels of area deprivation and increased SMM/MM ($p<0.01$)

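### Unless a woman states suicidal thoughts, Section 5.4 answers a positive depression screen only by email to a mailbox covered in business hours, with no contact time stated

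*Combined protocol and SAP*

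**What the plan says.** Section 5.4 (DHI intervention Overview) describes text links to educational content and, in addition, a validated depression screen sent during pregnancy and postpartum. It routes alerts as follows: "any alerts will be fielded to the POPPY email address covered by our research team during business hours". The depression screen is its worked example. For a positive result the text reads: "an alert will be emailed to the POPPY Email address and our team member will contact the patient and provide clinical resources". No time is attached to that contact, and no out-of-hours cover is described.

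Two safeguards do not depend on the mailbox:

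- General advice: "The messages urge the participant to call the OB/GYN clinic or present to the UAB MEU if there are any concerns".
- Participants who state that they are considering suicide: "they are instructed to call 988 and to present to the MEU or the nearest emergency room immediately". An email also goes to the same mailbox and the team follows up, again with no time given.

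For the educational links, Section 5.4 says that "the link and message expire in 24 hours". It does not say whether the screen link expires in the same way.

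Section 4.2 allocates "10 to usual care, 10 to DHI, 10 to CHW, and 10 to DHI + CHW". Section 1.5 adds: "A manual of operations supplements the protocol with detailed specifications of the study procedures". That manual was not among the documents reviewed.

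**The concern.** The study itself puts this screen in front of women, so it takes on the task of responding when one is positive. As written, a woman who screens positive without stating suicidal thoughts is not shown anything specific to her result, and the staff response begins only when someone reads the mailbox. If she answers on a Friday evening, that may not be until Monday, and nothing in the protocol says how soon she must then be contacted. Section 5.4 also allows the DHI to run for up to 3 months after a fetal demise or the loss of a baby, so the screened group can include recently bereaved women.

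The stake is participant safety, not the validity of an estimate. The missing deadline alone would be a matter of detail that the manual may supply. What makes the point worth raising is that the routing rule is explicit, and that its longest wait can be shortened without adding staff.

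**Working it through.** The plan gives no figure to reproduce. The check is a comparison of the response paths, followed by clock arithmetic.

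**Response paths in Section 5.4**

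| Event | Immediate instruction to the woman | Staff response | Time stated |
|---|---|---|---|
| Any concern | Standing advice: clinic or MEU | None described | Not applicable |
| Positive screen, no suicidal statement | None specific to the result | Email to mailbox, then contact | None |
| Suicidal statement | 988, MEU or emergency room | Email to mailbox, then follow-up | None |

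The second row is the gap. No other part of the protocol fills it. The research team that is on site around the clock (Section 5.2) is paged for eligibility screening. The 7-day limit in Section 5.6 is for submitting an adverse event form. Community health worker (CHW) contact is every other week and is not linked to DHI alerts.

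**Inputs**

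- Women receiving the screen: 10 (DHI) + 10 (DHI + CHW) = 20 of 40 planned (Section 4.2).
- Business hours: not defined. Assumed Monday to Friday, 8:00 or 9:00 to 17:00.
- Screen link expiry: not stated. Assumed 24 hours under the proposed rule, as for the educational links.

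**Longest wait until staff see an alert, as written**

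- Friday 17:00 to Monday 8:00: 7 + 24 + 24 + 8 = 63 hours. To Monday 9:00: 64 hours.
- If Monday is a public holiday: 63 + 24 = 87 hours, or 64 + 24 = 88 hours.
- Uncovered share of the week: (168 − 45)/168 = 123/168 = 73%, or (168 − 40)/168 = 128/168 = 76%.

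**Longest wait for a screen answer under the proposed send rule**

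The screen goes out at opening, and the link closes at the same hour next day.

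- An answer during covered hours reaches an open mailbox.
- An answer after closing waits at most from 17:00 to the next opening: 7 + 8 = 15 hours, or 7 + 9 = 16 hours.
- A plain Monday-to-Thursday rule is not enough. If the next day is a holiday, the wait becomes 15 + 24 = 39 hours, or 16 + 24 = 40 hours. Sending only when the next day is also a business day keeps the maximum at 15 to 16 hours.

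**Why the deadline needs a starting point**

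Suppose the rule were the end of the next business day after arrival. A screen sent on Thursday at 8:00 and answered on Friday at 7:00 would be due by Monday 17:00, which is 72 + 10 = 82 hours later. If contact is instead due by close of the business day on which the alert is first seen, and alerts are seen at opening, the longest time from a screen answer to contact is 15 + 9 = 24 hours, or 16 + 8 = 24 hours.

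**The case against.** The strongest reply is that the urgent case is already covered: a suicidal statement brings an immediate instruction that does not wait for the mailbox, and every participant is told where to go with concerns. The manual may set a call-back time, and that is a natural place for one. Nor is the DHI screen the only depression check: the visit schedule has a PHQ-9 at four timepoints, and half of the DHI women also have a CHW. Nothing in the documents shows that a weekend wait for a call to a non-suicidal woman is unsafe.

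Much of this stands. It limits the point to positive screens without a suicidal statement and to what the protocol itself says. It does not remove the point: standing advice relies on the woman to act, and neither the PHQ-9 visits nor the CHW contacts are a response to an alert.

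Three stronger readings are tempting, and the documents do not support them:

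- A reader might infer that suicidal women are left without help until Monday. Section 5.4 says otherwise; what can wait is the staff check that they sought care.
- A reader might set the 63 to 64 hours against the CHW entry in Table 2, "Follow-up within 48 hours after notification of birth", and conclude that the protocol breaks its own standard. That clock starts when staff are notified and concerns a different task. The 63 to 64 hours is the time before staff see anything.
- A reader might say that the pilot loses a feasibility benchmark. The aims in Section 1.4 are acceptance and use, enrollment, and outcome incidence. Alert timeliness is not among them, so no stated aim fails.

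Objections to the remedy also have force. The send rule bounds only answers to the screen; other alerts could still wait a weekend. It rests on a 24-hour expiry that the protocol states only for educational links. The Aim 1 interviews in Section 3 report shared phones, changing numbers and unreliable data access, so a newly imposed expiry could lower completion.

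**Conclusion.** The point holds in a limited form. The protocol states a routing rule under which a positive depression screen without a suicidal statement produces only an email to a business-hours mailbox and later staff contact at no stated time. Under the assumed hours, the longest ordinary wait before staff see the alert is 63 to 64 hours, in a group of 20 planned women. No number or probability of delayed alerts can be given, because the documents do not state the send schedule, the number of screens or the share positive.

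The conclusion covers the protocol alone. If the manual already sets a contact time, the deadline part reduces to a cross-reference; the automatic message and the send schedule would still be worth adding unless the manual has them too. This is a recommended safety improvement. It does not show that participants are unprotected.

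**What to change.** Make three changes in Section 5.4:

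1. Show every woman who screens positive an immediate automatic message giving the clinic, MEU and 988 routes, whether or not she mentions suicide.
2. Send the screen at opening time, only on a business day followed by another business day (ordinarily Monday to Thursday). Confirm that the screen link expires after 24 hours, or set it to do so.
3. State a contact deadline, or cite the manual section that sets it, running from when the mailbox is next covered: for example, by close of the business day on which the alert is first seen. Log the time of each alert and of each contact. Apply the deadline to all alerts, since the send rule bounds only screen answers.

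The text cost is a few sentences, one added platform message and a fixed send schedule, with no extra staff. This assumes that the platform can schedule around holidays and add the message, which the documents do not confirm. The practical cost is about four send mornings a week, repeat sends to women who miss the 24-hour window, and possibly lower completion if the expiry is new. Paging the on-site research team out of hours could be explored, but the protocol assigns that team's page to eligibility screening.

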5.4 Virtual Visits (for CHW) if applicable

If needed, the CHW will initiate a virtual visit in place of an in-person visit upon request by the participant. Virtual visits can be conducted by phone, video chat applications, computer-based programs (i.e. Zoom, Microsoft Teams, WebEx), or other platform that the site or participant prefers. During the virtual visits, baseline and home assessments, questionnaire will be asked of the participant, educational information and reminders will be given. We will ask about any new diagnoses or medications.

5.5 In-person Visit / Procedures

Here is the summary of the assessment visit across the enrollment

	Enrollment	28 – 32 weeks	Delivery Discharge / Neo Discharge	Postpartum Visit
Screening and Randomization Form	X			
Baseline Data Form including:	X			
Demographics	X			
Medical history	X			
Food insecurity	X			
Housing stability	X			
Social support	X			
Neighborhood / social environment	X			
Perceived Healthcare Access	X			
Everyday discrimination scale	X	X	X	X
Experience of discrimination	X	X	X	X
PHQ-9	X	X	X	X
Perceived Stress Scale	X	X	X	X
MORI Form	X	X	X	X
Prenatal course, breastfeeding plans		X		
Health literacy		X		
L & D Form (include prenatal course/complications)			X	
Miscarriage or early termination form	X			
Neonatal Form			X	
NICU Form			X	
Maternal Postpartum Follow up				X
Neonatal Readmission				X
Neonatal Well Being (combine with readmission?)				X
Intervention satisfaction form				X
SAE Form	X	X	X	X

Protocol Violation Form	X	X	X	X
-------------------------	---	---	---	---

***Items in **blue** denote common data elements across the EQUATE Network endorsed by the Social Determinants of Health Core

Medical history and questionnaire administration will be completed by site investigator or a trained delegate. Patients will be encouraged to have all medication present. In addition, participants will be asked to sign a medical record release so that medical records can be obtained and reviewed by the study team if not previously done.

